6.3.10.2. Hepatitis B Screening and Monitoring

Exclude subjects who are HBsAg positive, regardless of other hepatitis B serologies. If a subject is HBsAg negative and anti-HBc positive, perform HBV DNA. Exclude subjects who are HBV DNA positive.

** In Japan, if a subject is HBsAg negative, anti-HBc (HBcAb) negative, but HBsAb positive, an HBV DNA test will be performed and the subject will be excluded if results are positive (refer to Appendix 2).**

Subjects who are HBsAg negative, anti-HBc positive, and HBV DNA negative may be included in the study, but must undergo HBV DNA PCR monitoring at a minimum of every 12 weeks during the Treatment Period and for 6 months after the last dose. Consult with a physician experienced in the care and management of subjects with hepatitis B to manage/treat subjects who are anti-HBc positive. Antiviral therapy to be initiated if required.

Table 6-6 Hepatitis B Virus Test Result Scenarios for Subject Eligibility

HBsAg	anti-HBc (HBcAb)	HBsAb	HBV DNA	Subject Eligibility and Monitoring
All subjects:				
+ / -	+ / -	+ / -	positive	Exclude subject if positive at screening; discontinue study treatment if positive during study
positive	+ / -	+ / -	+ / -	Exclude subject if positive at screening
negative	positive	+ / -	negative	May enroll subject with physician consult and HBV DNA monitoring during study
Additional for Japan: negative	negative	positive	negative	May enroll subject with physician consult and HBV DNA monitoring during study

+ / - = either positive or negative test result

Abbreviations: HBcAb=hepatitis B core antibody; HBsAb=hepatitis B surface antibody; HBsAg=hepatitis B surface antigen; HBV=hepatitis B virus.

If a subject becomes HBV DNA positive during the course of the study, notify the medical monitor. Discontinue further treatment with investigational product and continue to follow the subject for safety as part of the Follow-up Period.

Extra visits outside those defined in the protocol may be needed for subjects who require hepatitis monitoring.

6.3.11. Other Safety Outcomes

6.3.11.1. Vital Signs

The following vital sign assessments will be measured by the investigator or medically qualified designee at the visits described in [Table 6-1](#):

- Sitting systolic and diastolic blood pressure after at least 5 minutes of rest. Use the same arm at each visit.
- Heart rate in the sitting position and at the time of the blood pressure measurement.
- Temperature.

6.3.11.2. Twelve-lead Electrocardiogram (ECG)

[figure not shown]
The investigator or medically-qualified designee will perform a standard 12-lead ECG as part of the Screening assessments. The ECG should be obtained as per the study center's usual practice. The investigator or medically-qualified designee will evaluate the ECG

for any abnormalities that should exclude the subject from the study. If the QTc exceeds ≥ 450 msec (≥ 480 msec for subjects with a bundle branch block), the subject will be excluded from participation in the study.

Ofatumumab, by its mechanism of action (lysis of CD20+ B-lymphocytes), does not affect QTc; therefore, QTc is not routinely monitored during this study. A repeat ECG will be obtained at Week 60 or early withdrawal.

6.3.12. Medical Device Incidents

** In Japan, medical devices that are approved in other countries but not approved in Japan will be provided by Novartis for use in this study. Refer to [Appendix 2](#) for medical device incident definitions and details on documenting, reporting, and follow-up of device incidents.**

6.5. Pharmacokinetics

The following pharmacokinetic endpoints will be evaluated, as data permit:

- Plasma (trough) concentrations of ofatumumab
- Exposure-response relationship

For subjects in the pharmacokinetic-pharmacodynamic substudy: pharmacokinetic endpoints will include model-based estimation of the following, as data permit:

- Maximum ofatumumab concentration (C_{max})
- Time of maximum concentration (T_{max})
- Area under the time-concentration curve (AUC)

Data permitting, there will also be an examination of the effect of demographic factors, including baseline covariates, on the pharmacokinetic endpoints.

Plasma analysis will be performed under the control of Novartis. The details of sample collection, processing, storage, and shipping are included in the [REDACTED] investigator manual. Concentrations of ofatumumab will be determined in plasma samples using the currently approved bioanalytical methodology. Raw data will be archived at the bioanalytical site, as per Novartis protocol.

Once the plasma has been analyzed for ofatumumab, any remaining plasma may be analyzed for other compound-related metabolites and the results reported under a separate Novartis protocol.

6.6. Pharmacodynamics

The following pharmacodynamic endpoints will be evaluated:

- Change from baseline in B-lymphocyte counts in peripheral blood.
- Time to repletion of CD19+ B-cells to either \geq baseline level or \geq LLN, whichever is lower.
- B-cell depletion and re-population as measured by CD19+ peripheral blood B-lymphocyte count via routine fluorescent activated cell sorting analysis.
- *For subjects in the pharmacokinetic-pharmacodynamic substudy:* CD19+ peripheral blood B-lymphocyte count via routine fluorescent activated cell sorting analysis with subsets including, but not restricted to, naïve and memory phenotypes.

6.7. Pharmacogenetics (PGx)

Information regarding pharmacogenetic (PGx) research is included in [Appendix 1](#).

7. DATA MANAGEMENT

For this study subject data will be entered into GSK-defined eCRFs, transmitted electronically to Novartis or designee and combined with data provided from other sources in a validated data system.

Management of clinical data will be performed in accordance with applicable Novartis standards and data cleaning procedures to ensure the integrity of the data, eg, removing errors and inconsistencies in the data. Adverse events and concomitant medications terms will be coded using the Medical Dictionary for Regulatory Activities (MedDRA), the World Health Organization Drug Dictionary, and an internal validated medication dictionary. An appropriate medical dictionary that covers all approved drugs in studies where Japan is participating will be referenced. Electronic CRFs (including queries and audit trails) will be retained by Novartis, and copies will be sent to the investigator to maintain as the investigator copy. In all cases, subject initials will not be collected or transmitted to Novartis according to Novartis policy.

8. DATA ANALYSIS AND STATISTICAL CONSIDERATIONS

8.1. Hypotheses

The overall null hypothesis is that there is no difference in time to SR on minimal steroid therapy by Week 60, and there is no difference in duration of remission on minimal steroid therapy between subjects in the ofatumumab SC group versus subjects in the placebo group. The alternative hypothesis is that ofatumumab SC is superior to placebo in at least one of the co-primary endpoints.

8.2. Study Design Considerations

8.2.1. Sample Size Assumptions

Assuming that the proportion of subjects achieving SR on minimal steroid therapy status is 54% and 80% in the placebo and the ofatumumab SC groups, respectively [Beissert, 2010], with proportional hazards across the various strata, a sample size of 68 subjects per group will give $\geq 90\%$ power for a statistically significant difference between the two groups in time to SR on minimal steroid therapy, using a two-sided 0.05 level of significance. Note that for the purpose of sample size calculation of time to SR, “survival” means: “Not in SR”, and hence $(100-54=)$ 46%, and $(100-80=)$ 20% are the survival rates for the placebo and ofatumumab SC treatment groups respectively needed to calculate sample size for the log-rank test. The study is designed to detect a hazard ratio of 0.48248 (median time to response on ofatumumab SC/median time to response on placebo). It is assumed that no more than 13% of the subjects in both groups will be lost to follow-up before their Week 60 visit. With the projected 54% and 80% SR rates in the placebo and active groups respectively, a total of approximately 80 subjects with SR in both treatment groups combined are needed at the end of the study. Because this study has 2 co-primary efficacy endpoints, an evaluation of the overall power to detect at least one significant endpoint was made using simulations. The analysis proposed for the

co-primary endpoints is a sequential test based on the method of Alosch and Huque [Alosch, 2010]. Results of the simulations are displayed in Table 8-2.

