8.2.2. Sample Size Sensitivity

The sample size projected for this study is based on the assumption of 54% and 80% SR rates in the placebo and ofatumumab SC treatment groups respectively. For a log rank test, the projected hazard ratio is 0.48248 (ofatumumab SC/placebo) and the projected number of subjects with SR on minimal steroid therapy is 80. If the hazard ratio is indeed 0.48248, but the response rates in both groups are lower, then more subjects will need to be enrolled in order to have at least 80 subjects with SR at the end of the study.

Table 8-1 shows the sensitivity of the sample size to the response rates in each treatment arm, assuming a hazard ratio of 0.48248.

Table 8-1 Sample Size Sensitivity

Placebo Response Rate	Ofatumumab SC Response Rate	Total Sample Size Needed for At Least 80 Responses (Assuming a 13% Dropout Rate)
0.42	0.68	166
0.44	0.70	160
0.46	0.72	154
0.48	0.74	148
0.50	0.76	144
0.52	0.78	140
0.54 ^a	0.80	136

a. Projected for the study.

The primary analysis is based on a sequential test of the 2 co-primary endpoints: time to SR on minimal steroid therapy, and duration of remission, using the method of Alosch and Huque [Alosch, 2010], described in detail in Section 8.3.6.5. In this method, a sequential testing of the co-primary endpoints is made using critical points that provide consistency results for the 2 co-primary endpoints. Two parameters were considered in the simulation: time to SR on minimal steroid therapy, and duration of remission on minimal steroid therapy. Simulations were made using an exponential time to event (time to remission, and time to flare), and using the protocol definitions of SR and duration of remission. The ranges of values for these parameters were selected to provide approximately 54% and 80% remission rates in the placebo and active groups respectively, assumed for this study.

Table 8-2 Overall Power for the Co-primary Endpoints

Parameter	Placebo	Ofatumumab SC	Overall Power
Time to remission (weeks)	28	16	95%
Duration of remission (weeks)	8	17	
Time to remission (weeks)	32	16	90%
Duration of remission (weeks)	9	17	
Time to remission (weeks)	44	20	93%
Duration of remission (weeks)	10	19	

Abbreviation: SC=subcutaneous.

Note: Based on simulation of 100 trials with 59 subjects per group.

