8.2.3. Blinded Sample Size Re-estimation

The power of 90% for this study assumes that 80 subjects will have SR on minimal steroid therapy by the end of the study. This number will be monitored in a blinded way, and if necessary, more than 136 subjects will be randomized to ensure that at least 80 subjects will have SR on minimal steroid therapy at the end of the study. Because the sample size re-estimation is done in a blinded manner, based on the total number of SRs, no penalty for type-1 error inflation is warranted. The reporting and analysis plan (RAP) will specify the method of monitoring and adjustment to the sample size.

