8.3.4. Interim Analysis

An interim analysis for futility will be conducted when 60 events of SR on minimal steroid therapy have been observed. The analysis will be conducted by an unblinded statistician not involved in the conduct of the study and results will be presented to the IDMC. A conditional power analysis will be conducted based primarily on projecting the observed trend of the difference between ofatumumab and placebo in time to remission on minimal steroid therapy. If the analysis indicates that the conditional power for a positive outcome for time to remission on minimal steroid therapy ($p < 0.025$ one-sided) is less than 30%, the IDMC will communicate to designated Sponsor's representatives that the study is unlikely to meet its primary objectives. The Sponsor may evaluate additional information such as pharmacokinetics and pharmacodynamics and make a final decision regarding continuation of the study.

If enrollment is substantially slower than anticipated and/or the rate of SRs is much smaller than projected, consideration will be given to performing the interim analysis for futility at an earlier time point. If a decision is made to perform an early interim analysis, the IDMC will be notified of this decision and preparation will be made for an unscheduled IDMC meeting. After review of the interim data, the IDMC may:

- Recommend continuing the study as planned.

- Determine that continuation of the study is unlikely to reach a successful conclusion on the basis of the slow enrollment and/or low rate of remissions and thus recommend stopping the study early for futility.

The interim analysis will not be used to stop the study early for a positive outcome; therefore, no adjustment to the final analysis type-1 error is indicated. Details of the interim analysis will be specified in the IDMC charter, as well as in the RAP.

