8.3.6.5. Efficacy Analyses

Graphical displays and tables will present and summarize all efficacy measures over the course of the study. Means, SDs, medians, maximum, minimum, and number of subjects will summarize continuous data. Categorical data will be summarized by counts and percentages. Confidence intervals (Cis) (95%) and p-values will be displayed where applicable.

Primary Endpoint Analyses

Baseline prednisone/prednisolone dose and disease duration will be used to stratify all primary and secondary analyses. The primary analysis for the co-primary endpoints will use the ITT population.

The co-primary efficacy endpoint of time to SR on minimal steroid therapy by Week 60 will be analyzed using a log-rank test stratified by baseline prednisone/prednisolone dose and disease duration strata. Subjects who discontinue prematurely (prior to Week 60) will be censored at the time they discontinued. Subjects who reach Week 60 without remission will be censored at their last visit. Calculation of time to SR will be made from randomization date to the first time the subject was in remission for 8 consecutive weeks while on minimal steroid therapy and sustained that remission until Week 60.

The co-primary endpoint of duration of remission on minimal steroid therapy will be analyzed using a rank analysis of covariance (ANCOVA) [Stokes, 2000], with treatment as a main effect, and baseline prednisone/prednisolone dose and disease duration strata as covariates. If a subject went into remission, then relapsed, and then went into remission

again (or possibly more than 2 episodes of remission), the duration of remission will be the total time (sum) of all periods of remission while on minimal steroid therapy up to Week 60. If a subject discontinued the study prior to Week 60, the subject will be considered as not in remission from the last known visit till Week 60.

To protect the overall type-1 error at 0.05 (one-sided 0.025), the analysis of the co-primary endpoints will follow the procedure proposed by Alosch and Huque [Alosch, 2010]. In this procedure, a consistency criterion is applied, so that the co-primary endpoints can be deemed significant only if one of the following events occur:

1. The time to SR on minimal steroid therapy is significant at one-sided 0.02. If significant, then duration of remission on minimal steroid therapy is tested at one-sided 0.025.

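### The stated power of at least 90% for time to sustained remission is not for the rule that tests it, the futility rule names a different endpoint, and 0.48248 is mislabelled as an ofatumumab/placebo hazard ratio

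*Protocol*

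**What the plan says.** Protocol 8.2.1 gives at least 90% power with 68 subjects per group for a log-rank difference "in time to SR on minimal steroid therapy, using a two-sided 0.05 level of significance". The inputs are "54% and 80% SR rates in the placebo and ofatumumab SC treatment groups respectively", at most 13% lost before Week 60, and the statement that "a total of approximately 80 subjects with SR in both treatment groups combined are needed at the end of the study". Section 8.2.3 repeats the claim: "The power of 90% for this study assumes that 80 subjects will have SR on minimal steroid therapy by the end of the study".

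The test is set out in Protocol 8.3.6.5. Its first route to success is: "The time to SR on minimal steroid therapy is significant at one-sided 0.02". If the one-sided p-value lies between 0.02 and 0.025, time to SR is rejected only when duration of remission passes an adapted level that falls from 0.025 to 0.018. Above 0.025, time to SR cannot be rejected.

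Protocol 8.3.4 schedules the futility analysis at 60 SR events, but the quantity compared with 30% is the "conditional power for a positive outcome for time to remission on minimal steroid therapy", at one-sided 0.025. Section 6.2.2 lists time to remission as a secondary endpoint, distinct from time to SR.

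On the effect size, 8.2.1 says "The study is designed to detect a hazard ratio of 0.48248" and explains it in brackets as median time to response on ofatumumab over that on placebo. Section 8.2.2 says: "For a log rank test, the projected hazard ratio is 0.48248 (ofatumumab SC/placebo").

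**The concern.** Sizing, final test and futility rule do not describe the same success criterion for the same co-primary endpoint. The power statement uses 0.025, the procedure's unconditional level is 0.02, and the conditional power is defined on another endpoint. At stake are a quoted power that is somewhat optimistic for time to SR, and a rule under which the sponsor could be told that the primary objectives are unlikely to be met on the evidence of a secondary endpoint.

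Two further features need checking. SR must be maintained to Week 60, so a subject who leaves cannot meet the definition, yet that subject counts in the log-rank risk set until censored. Simple inflation of the sample size ignores this. Also, the event here is a benefit, so a hazard ratio below 1 for ofatumumab over placebo would favour placebo.

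**Working it through.** **1. Effect size.** The proportions not in SR are 46% (placebo) and 20% (ofatumumab), from 8.2.1. Then ln(0.46)/ln(0.20) = 0.48248, which is the placebo hazard over the ofatumumab hazard. Its inverse, 2.07, is the ofatumumab/placebo hazard ratio for SR. With exponential times, 0.48248 is also the ofatumumab/placebo ratio of medians. Taken literally as an ofatumumab/placebo hazard ratio, it would give an SR rate on ofatumumab of 1 − 0.46^0.48248 = 31%, not 80%.

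**2. Reproducing the plan.** Schoenfeld events for 90% power: 4 × (1.960 + 1.282)² / (ln 0.48248)² = 79.1, so 80. Expected events: 136 × 0.87 × 0.67 = 79.3, where 0.67 averages 54% and 80%. Power is Φ(√(d/4) × 0.7288 − z):
- 79.3 events: Φ(3.245 − 1.960) = 90.1%
- 80 events: 90.3%

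The stated figure reproduces.

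**3. The level actually used.** At one-sided 0.02, z = 2.054: 88.3% at 79.3 events and 88.6% at 80. The route between 0.02 and 0.025 can only add to this, and cannot take power above the 0.025 value. The full rule therefore lies between about 88% and 90%, depending on the effect on duration and on the correlation. Simulating the full rule at 80 events, over a range of both, gave 88.6% to 90.1%.

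**4. Leavers.** Suppose leavers never count as SR but stay at risk until they leave. The event count is still about 79, but the contrast weakens. In the extreme where all leave near Week 60, the SR proportions are 0.87 × 54% = 47.0% and 0.87 × 80% = 69.6%, and the ratio in step 1 becomes ln(0.530)/ln(0.304) = 0.53. Log-rank simulation (20,000 trials, 68 per group, exponential times, 13% leaving; leaving times are not given in the documents):

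| Assumption | 0.025 | 0.02 |
|---|---|---|
| All leave at time 0 | about 90% | about 88% |
| Leave uniformly over 60 weeks | about 87% | about 85% |
| All leave near Week 60 | about 82% | about 80% |
| Uniform, SR reached before leaving counted | about 92% | about 91% |

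With 8% leaving uniformly instead of 13%, and no SR for leavers, power is about 90% and 88%.

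**5. Futility.** Purely as an illustration, take the rule as binding and applied to SR. At 60 of 80 events (t = 0.75), current-trend conditional power falls below 30% when Z < √0.75 × (1.960 − 0.5 × 0.524) = 1.470. Under the design effect the mean of Z is 3.259 × 0.866 = 2.823, so the chance of stopping is Φ(−1.35) = 8.8%. Power would then be 86.1% at 0.02 and 87.3% at 0.025, before any allowance for leavers.

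**The case against.** There is a good case that little is wrong. The calculation in 8.2.1 is correct for the test it names, and blinded re-estimation in 8.2.3 protects the 80 events. The trial's success criterion is superiority on at least one co-primary (8.1), and Table 8-2 gives simulated power of 90% to 95% for that. The 13% is an upper bound. SAP 11.1.1 censors leavers who have not achieved remission on leaving, which hints that others might count as events. The bracket in 8.2.1 shows what 0.48248 means. Finally, the SAP drops the interim analysis (4.1), the sizing sections (5) and the multiplicity procedure (8.3, 11.1.3).

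Most of this limits the size of the point without removing it. Table 8-2 answers a different question from the power for time to SR, and rests on only 100 simulated trials. Holding 80 events does not repair the leaver effect, because the loss in step 4 is not an event shortfall. The SAP wording on leavers conflicts with the definition of SR and with the projection of about 80 events, which already excludes them. The bracket in 8.2.1 does not correct the label in 8.2.2.

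Two stronger readings are tempting. A reader might infer that power is really about 85% because of the 0.02 level and the futility look. The documents do not support that: the 0.02 level costs at most about 1.7 points, and under 8.3.4 the committee only informs the sponsor, who decides, so the protocol fixes no power loss. The 85% comes from one assumed pattern of leaving. A reader might also infer that the sample size was computed in the wrong direction. It was not; only the label is wrong.

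**Conclusion.** The mismatch stands, and it is small. By the protocol's own formula, power for time to SR under the stated procedure is about 88% to 90%, against the claimed minimum of 90%. If all of the 13% leave uniformly, never count as SR and remain at risk until they go, it is about 85% at 0.02 and 87% at 0.025. The 0.02 figure runs from about 80% to 88% across leaving times, and is about 91% if SR before leaving counted.

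The futility rule is inconsistent as written: its trigger is SR and its conditional power is for remission. The rationale recorded for Amendment 3 in Appendix 15 says the futility analysis should rest on sustained remissions, so this looks like wording left behind. The hazard-ratio label in 8.2.2 is wrong for the event SR. It could mislead a reader who sets the design value of 0.48 beside the Cox hazard ratio planned in SAP 11.1.1, where an ofatumumab/placebo value above 1 is benefit.

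With 69 randomized, and the interim analysis, sizing sections and multiplicity procedure all dropped, none of this changes the final analysis.

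**What to change.** Correct the description of the design, in the study report or wherever these figures are quoted:

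- State power for time to SR together with the level (one-sided 0.02 alone, or the full two-endpoint rule) and the assumption about when leavers go and whether they can count as SR. Cite Table 8-2 separately, as power for at least one co-primary.
- State that the conditional power in 8.3.4 is for time to SR, matching its trigger.
- Relabel 0.48248 as the ofatumumab/placebo ratio of median times to SR, and give the ofatumumab/placebo hazard ratio as 2.07, with values above 1 favouring ofatumumab.

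The cost is a few sentences and a slightly less favourable power figure. No patients are added and no SAP analysis changes.
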